Binary endpoints, including primary endpoint, are analyzed using Chi-2 test. Continuous data are assessed for parametric distribution and analyzed with Student's T-test on logarithmic transformed data in case of non-parametric distribution.

Level of statistical significance is set to 5%.

A logistic prediction model will be developed. Dependent variable is intubation. Independent variables are age (continuous), FLUS result (Binary or ordinal), SARS-CoV-2 status (Binary) and peripheral oxygen saturation (continuous).

The data set will be divided in two. One is used for model development and one is used for validation of the model. Geographic external validity is tested. Internal validity is tested with bootstrapping method. Sensitivity, specificity and ROC AUC is calculated.

Sample size

No prior publications are available for sample size estimation.

For the prediction model we wish to include 10-15 events per independent variable, 50-75 events. From early estimations about 20% of admitted patients requiring intubation our estimate is 375-400 participants.

Inclusion period

An end date is set to May 15 2020. If COVID-19 pandemic is ongoing at this time point the study may extent.

Blinding

Ultrasound film clips are analyzed blinded to other variables.

Plan for publication

Data analysis is estimated to end July 1. 2020. Article submission is estimated to October, 2020.

Preliminary data analysis

Available data will be analyzed soon after 15. May.

Ethical considerations

FLUS is without any risk to patients. COVID-19 is an infectious disease and isolation is needed. Contamination during the study needs to be avoided. For this reason, FLUS is only performed by the physicians who are required to see the patient regardless of this study. The ultrasound equipment is cleaned after each examination in accordance with local guidelines.

Legal regulations

In Denmark the study is classified as a quality assurance project. Arrangements and permission to access to patient files in each site is required. According to guidance from the legal office at Region Midt a data management agreement is not needed.

International data agreements are required to data transfer from international sites to Denmark.

All international sites must adhere to local regulation. Responsibility of this is on the international site.

Publication

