ITA admission	Univariat logistiscal regression	Variable: ita_in flusmed	
	Multivariate logistical regression	Variable: ita_in, Flusmed, alder, køn, sat	, if behandlingsloft_ita ==0
Ventilator treatment	Univariat logistical regression	Variable: respirator_beh flusmed	
	Multivariate logistical regression	Variable: respirator_beh Flusmed, alder, køn, sat	, if behandlingsloft_resp ==0

Continuous variables are assessed for parametric distribution with quartile-quartile plots. Medians, interquartile ranges or means and standard deviations and ranges are reported according to parametric distribution. Students' t-test or Mann-Whitney U test is used as it was considered appropriate to evaluate differences between groups. The statistical significance is set to 5%. All data are handled in Excel (Microsoft) and REDCap (hosted at Aarhus University). All analyses are performed using Stata 14.2 (StataCorp, USA).

Building Prediction Models

Prediction models are based on multivariable logistic regression and preselected variables. The variables are sex, age, relevant comorbidity, oxygen administration and the mean-FLUS score. The selection of these variables is based on published data and clinical experience available to the study group during the study design stage. Explanatory variables are examined to decide cut-points, scales or the need for transformation. Variables are limited and prioritized to avoid overfitting or underfitting, respecting the study population size. Every included variable require at least 15 events.

The dependent variable is the primary outcome of interest: the COVID-19-related need for mechanical ventilation in the main analysis. Secondary outcomes are analyzed using the same logistic regression model, except for the outcome on high-flow oxygen treatment. The explanatory variable on oxygen administration is considered closely related to the outcome and is thus excluded from this analysis.

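### The protocol sizes the prediction model on 50 to 75 events in the whole data set, then divides the data without giving a ratio, a basis or a stated allowance in N

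*Protocol*

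**What the plan says.** The protocol's Sample size section sets the target: "For the prediction model we wish to include 10-15 events per independent variable, 50-75 events". It then converts events to participants: "From early estimations about 20% of admitted patients requiring intubation our estimate is 375-400 participants".

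Its Data analysis section specifies a logistic model for intubation with four predictors (age, FLUS result, SARS-CoV-2 status and oxygen saturation). It continues: "The data set will be divided in two. One is used for model development and one is used for validation of the model". The next sentences read: "Geographic external validity is tested. Internal validity is tested with bootstrapping method". Neither document gives the proportions of the division, how patients are assigned to the two parts, or any increase in N on account of it.

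The SAP, which carries the same date, mentions no division. Its table lists for the ventilator model "Variable: respirator_beh Flusmed, alder, køn, sat" (mean FLUS, age, sex, saturation), restricted to patients without a ventilator treatment limit. Its section on building prediction models has another list: "The variables are sex, age, relevant comorbidity, oxygen administration and the mean-FLUS score". That section also sets a floor: "Every included variable require at least 15 events".

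The protocol's inclusion criteria cover both admitted patients with a positive test and people seen in COVID clinics or emergency departments for diagnostic work-up.

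**The concern.** The prediction model is the only stated basis for the sample size, and predicting respiratory failure is the first listed aim. The event target yields the lower stated N exactly when every participant contributes to fitting. Once part of the data is set aside, the events available for fitting shrink by an unstated amount. A reader cannot tell how many events the model is fitted on, how many predictors it can carry, or how many events remain to judge it.

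The two needs also compete at the planned N, because events reserved for validation are lost to development. With a total of 75 to 80, either the model is fitted on few events or its performance is estimated imprecisely.

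**Working it through.** **Inputs.** From the protocol: 10 to 15 events per variable, 50 to 75 events, about 20% intubated among admitted patients, N = 375 to 400, four listed predictors. From the SAP: at least 15 events per variable; five variables in its text if comorbidity counts as one. The split ratios, the AUC and the lower event rates below are assumptions.

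**1. Reproduce the plan's figure.** 50/10 = 75/15 = 5 variables. N = events/rate: 50/0.20 = 250 and 75/0.20 = 375. The lower stated N follows from the upper event target on undivided data. Expected events in total: 375 × 0.20 = 75; 400 × 0.20 = 80.

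**2. Development share needed.** For 50 events: 50/80 = 62.5% to 50/75 = 66.7%, leaving 30 to 25 for validation. For 75 events: 75/80 = 93.75% to 75/75 = 100%, leaving 5 to 0.

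**3. Expected events by assumed split.** Development events = N × 0.20 × development share; the rest go to validation.

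| Assumed split | Development events | Per variable, protocol's 4 | Per variable, 5 | Validation events | AUC half-width |
|---|---|---|---|---|---|
| 50:50 | 37.5–40 | 9.4–10.0 | 7.5–8.0 | 37.5–40 | 0.093–0.096 |
| 2:1 | 50–53.3 | 12.5–13.3 | 10.0–10.7 | 25–26.7 | 0.114–0.118 |
| 80:20 | 60–64 | 15.0–16.0 | 12.0–12.8 | 15–16 | 0.148–0.153 |
| None, all data | 75–80 | 18.8–20.0 | 15.0–16.0 | – | 0.066–0.068 |

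The last column is the 95% half-width for an assumed AUC of 0.75, as 1.96 times the Hanley-McNeil standard error. With e events, m non-events, B = A/(2−A) and C = 2A²/(1+A), the variance is [A(1−A) + (e−1)(B−A²) + (m−1)(C−A²)]/(em). For 2:1 at N = 375, e = 25 and m = 100: (0.1875 + 24 × 0.0375 + 99 × 0.0804)/2500 = 0.00362, and 1.96 × √0.00362 = 0.118. The protocol sets no precision target, so this column is illustrative. The all-data row is sampling error only; the optimism correction comes from the bootstrap.

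**4. Chance of at least 50 development events** (binomial, 20%): 50:50, 0.017 (n = 188) to 0.049 (n = 200); 2:1, 0.525 (n = 250) to 0.721 (n = 267); 80:20, 0.938 (n = 300) to 0.981 (n = 320).

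**5. The SAP's floor as a cap on variables.** Events/15, rounded down: 37.5–40 events allow 2 variables, 50–53.3 allow 3, 60–64 allow 4, and 75–80 allow 5.

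**6. Mixed cohort.** If the overall rate were 10 to 15%, total events would run from 375 × 0.10 = 37.5 to 400 × 0.15 = 60 before any division. At 15 per variable that carries 2 (37.5/15 = 2.5) to 4 (60/15 = 4) variables on all data.

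**The case against.** The best defence is that this is a reporting gap and not a sum gone wrong. The sample-size arithmetic reproduces. N = 375 also equals 250/(2/3), that is, 50 development events at a 2:1 split, so a built-in allowance cannot be ruled out. Splits from 2:1 to 80:20 stay inside the stated 50 to 75 and give at least 10 events per variable for the protocol's four predictors. All of that stands. A reader might infer that the study is too small for its model, but the documents do not support this: only a development share below about 62.5 to 67% misses the lower target, and no share is stated.

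A reader might also infer that the SAP's 15-event rule is broken, because none of the splits considered reaches 75 events. That inference joins the SAP's rule to a division that only the protocol plans. On all data, at 20%, five variables at 15 each are just met in expectation (75 to 80). Nor does the SAP's limit on variables work only on undivided data; it can be applied equally to a development part, as step 5 shows.

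The division may be the geographic one, since the next sentence concerns geographic validity. The shares would then depend on recruitment by site and could not be fixed in advance. This is plausible, but the text does not say it. It would make naming the basis sufficient in place of a fixed ratio, with expected events still to be given.

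Finally, N is an estimate and inclusion may be extended. The extension depends on the pandemic continuing and not on an event count, so it does not secure the target.

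**Conclusion.** The concern holds as a gap between the event target and the planned division. At 20% and the planned N there are 75 to 80 expected events in all. Whether the development part reaches 50 to 75 turns on a ratio that neither document gives: 37.5 to 40 at an equal split, 50 to 64 from 2:1 to 80:20, with 15 to 27 then left for validation. Even at 2:1 with N = 375, the chance of reaching 50 is only about one half.

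Separately, the protocol and SAP disagree on whether there is a split, and between them give three predictor lists for ventilation. The number of events required is therefore not settled either. This is an inconsistency between the documents and not a failure of the SAP's own rule.

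The 20% is an assumption for admitted patients applied to a wider cohort. The range of 38 to 60 events rests on an assumed overall rate of 10 to 15%, which the documents do not give. The issue should be fixed but is confined to the prediction model; the chi-square primary analysis does not depend on it.

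**What to change.** Develop the ventilation model on all participants. Use the planned bootstrap to obtain optimism-corrected discrimination and calibration, repeating every modelling step (cut-points, transformations, any selection) in each resample. Assess geographic validity across sites or regions where events allow.

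If a geographic split is kept, state its basis, give the expected development and validation events, and apply the SAP's floor of 15 events per variable to the development part.

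In either case, align the protocol, the SAP table and the SAP text on one predictor list, one analysis population and one statement on whether the data are divided. State that the 20% refers to admitted patients, and give the expected events for the mixed cohort. If these are fewer than 75, the SAP's cap implies fewer than five variables.

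The cost is wording in both documents and some computing. The small downside is that no single untouched hold-out set remains. Fitting on all participants needs no extra patients. Keeping a split and still aiming for 50 to 75 development events at 20% would need N = events/(0.20 × development share): 500 to 750 at 50:50, 375 to 563 at 2:1, or 313 to 469 at 80:20.

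### The geographic validation of the intubation model has no calibration measure and no pre-set risk cut-off, so no planned measure could reveal a shift in absolute risk between regions

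*Protocol*

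**What the plan says.** The protocol's Data analysis section plans a logistic prediction model: "Dependent variable is intubation". The data are divided in two: "One is used for model development and one is used for validation of the model". Two kinds of validity follow: "Geographic external validity is tested" and "Internal validity is tested with bootstrapping method". The paragraph closes with the performance measures: "Sensitivity, specificity and ROC AUC is calculated".

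Neither the protocol nor the SAP states:
- a calibration measure (intercept, slope, plot, observed/expected ratio, Brier score or goodness-of-fit test);
- a cut-off on predicted risk, or a rule for choosing one;
- which statistic the bootstrap is to correct;
- the proportions of the split, or which sites or regions form the validation data;
- a criterion by which validation succeeds or fails.

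The SAP's section on building prediction models covers the choice of variables and outcome. It names no validation step and no performance measure. The cut-points it mentions concern the coding of explanatory variables, not predicted risk.

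**The concern.** A geographic validation asks whether a model built in one place works in another. It can fail in two ways: the ranking of patients can deteriorate, or the ranking can hold while the absolute risks are wrong. AUC addresses only the first. Sensitivity and specificity describe classification at one threshold, and a logistic model has neither until a threshold is set. If the threshold is chosen in the data being evaluated, both kinds of information suffer: the threshold moves to absorb any shift in risk, and the reported figures are optimistic.

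A difference in baseline risk is plausible here. The study is multicentre, uses convenience sampling and provides for international sites. It enrols both people being worked up for COVID-19 and admitted PCR-positive patients, and the protocol's intubation rate refers to admitted patients only. What is at stake is what the validation can conclude: carried out exactly as written, it could not tell readers whether the predicted risks are right in a new region.

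**Working it through.** **Inputs from the protocol.** Sample size section: "For the prediction model we wish to include 10-15 events per independent variable, 50-75 events" and "From early estimations about 20% of admitted patients requiring intubation our estimate is 375-400 participants". Performance measures: the three named in Data analysis.

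**Assumptions, not in the documents.** Half split. Normally distributed linear predictor, with SD 1.2 (AUC 0.78) or 1.4 (AUC 0.81). Regional risks of 5%, 10% and 40%, chosen for illustration.

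**1. The plan's own figure.** Participants = events / event rate. Taking 5 variables × 15 = 75 events, 75 / 0.20 = 375, the lower stated figure. 400 × 0.20 = 80 events. (The event range implies five variables; the protocol lists four. That does not affect this point.)

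**2. Validation events under a half split.** 375 × 0.20 / 2 = 37.5; 400 × 0.20 / 2 = 40.

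**3. Why AUC is blind to the shift.** Write predicted risk as 1 / (1 + exp(−(a + x))), where x is the patient's linear predictor and a the baseline. Replacing a by another value changes every risk but never the order of two patients. AUC is the probability that a case ranks above a non-case, so it is the same for the wrong risks and for the corrected ones. Simulation of 400,000 patients (SD 1.2, model developed at 20% risk) confirmed this to all digits in each region. Results for the unchanged model:

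| True risk | Mean predicted | Expected/observed | AUC | Sensitivity / specificity at fixed cut-off 0.20 |
|---|---|---|---|---|
| 20% | 20% | 1.00 | 0.777 | 0.709 / 0.700 |
| 10% | 20% | 1.99 | 0.784 | 0.757 / 0.660 |
| 5% | 20% | 3.94 | 0.790 | 0.786 / 0.640 |
| 40% | 20% | 0.50 | 0.772 | 0.616 / 0.775 |

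**4. What a fixed cut-off shows.** At 10% true risk, sensitivity moves by 0.757 − 0.709 = 0.048 and specificity by 0.660 − 0.700 = −0.040. Even with 37.5 events and 150 non-events, the standard errors are √(0.709 × 0.291 / 37.5) = 0.074 and √(0.700 × 0.300 / 150) = 0.037. The movement is about one standard error or less, and it does not show the size of the error. Patients flagged positive had a mean predicted risk of 37% and an actual risk of 20%. With SD 1.4, patients predicted at 30-40% had an observed risk of 16%.

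**5. What a cut-off chosen in the validation data shows.** With the maximum Youden index (sensitivity + specificity − 1) at 10% true risk, sensitivity and specificity were 0.696 and 0.721 for both the wrong and the corrected risks. Only the cut-off moved, from 0.235 to 0.105.

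**6. How much the cut-off matters.** With SD 1.4 and 20% risk, a cut-off of 0.5 gives sensitivity 30% and specificity 96%; a cut-off of 0.2 gives 74% and 72%. Choosing the Youden cut-off on 187 patients shows an average sensitivity of about 77% against a true 71% (Youden index 0.52 against 0.44).

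**7. Whether calibration would help at this size.** For a truly calibrated model and 188 validation patients, the 95% sampling range is about 0.74-1.26 for observed/expected and 0.63-1.50 for the slope. A two-fold overstatement has observed/expected of 1 / 1.99 = 0.50, outside that range. A modest error would not stand out.

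**The case against.** The strongest objections concern how far the omission reaches.

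- **No pass criterion.** A reader might infer that a miscalibrated model would be declared externally valid. The protocol does not say this; it says only that validity is tested and three measures are calculated. What can be said is that none of those measures would reveal the error.
- **Intended use.** A reader might infer that the model's probabilities are to steer resources. The protocol's Background speaks of identifying high-risk patients and of managing those without pneumonic FLUS findings as out-patients. That is stratification by FLUS finding, for which discrimination matters most. No clinical role is given to a model probability.
- **Regional rates.** The documents give one rate, about 20% of admitted patients. A shift is plausible, but they do not establish that it is the likely failure, and the regions above are scenarios.
- **Other failures are visible.** If predictor effects weaken to 0.6 of their size, AUC falls from 0.78 to 0.69.
- **Ambiguous sentence.** The three measures are not tied expressly to the geographic test, and sensitivity and specificity might partly mean binary FLUS against PCR and chest radiograph, which has its own built-in cut-off. The position of the sentence, directly after the validation steps, favours the model, and no other measure appears anywhere.
- **Noise.** The average Youden optimism of about 6 points is small beside sampling variation: with SD 1.45 and 187 patients, apparent sensitivity ranged from about 58% to 95%.

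All of these limit the claim. None supplies a calibration measure or a cut-off rule.

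**Conclusion.** The point holds as a gap in what the validation can show, and it should be corrected before analysis. Following the named measures exactly, a two-fold error in absolute risk would leave AUC unchanged and move sensitivity and specificity by about 4 to 5 percentage points at a fixed cut-off, or not at all if the cut-off is chosen in the validation data. Choosing it there also overstates sensitivity by about 6 points on average (77% against 71%).

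The blindness of AUC to a baseline shift is mathematical and needs no assumption. The sizes rest on the simulated predictor distribution, the half split and the illustrative regional risks. The documents do not support the stronger conclusions that the plan would certify a wrong model as valid, that patients would be managed on its probabilities, or that regional risks are known to differ. The primary Chi-2 comparison of binary FLUS with intubation is untouched.

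**What to change.** Add to the SAP's section on prediction models:

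1. In the validation part, report calibration-in-the-large (or observed/expected), the calibration slope and a calibration plot, each with 95% CIs, beside the AUC.
2. In the development part, report the bootstrap optimism-corrected AUC and calibration slope, which also settles what the bootstrap is for.
3. Set the predicted-risk cut-off in the development part by a rule written before analysis. Apply it unchanged to the validation part, with 95% CIs for sensitivity and specificity.
4. Report any recalibrated model as exploratory and not as validated. Do not make recalibration automatic whenever the intercept differs from 0 or the slope from 1: estimates always differ, and a truly calibrated model would give slopes of about 0.63-1.50. A model recalibrated on the validation part also has no independent data left to validate it.

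This needs no extra patients or data, only SAP wording and routine Stata output. Sensitivity and specificity may look slightly less favourable. Calibration will be imprecise with about 37-40 validation events (half split assumed). A cut-off set in as few development events will also be unstable: with SD 1.45, the Youden cut-off from about 37 events ranged from 0.11 to 0.35. The intervals should therefore be shown and the rule chosen with this in mind.

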Focused lung ultrasound for diagnosing and risk- stratification of patients with COVID-19 symptoms

April 8, 2020
NCT 04327674

Background

COVID-19 is defined as an infectious disease caused by SAR-CoV-2 virus. It results in pneumonia and sometimes respiratory failure. SARS-CoV-2 pandemic has led to massive strain on health care facilities. A large proportion of the population is at risk of COVID-19 and some estimates suggest that up to 15% will need hospitalization. Such number of patients strains the health care system to its maximum as capacity has limitations even in highly developed countries.

Early reports estimate that more than 80% of patients admitted to hospital with COVID-19 have abnormal findings on chest radiographs¹. Thus, imaging seems to be an important part of the diagnostic work-up. In most hospitals however, access to CT-scanning of the thorax of all patients with COVID-19 or with suspicion of COVID-19 is unrealistic due to restricted capacity. Chest radiographs are faster and easier to do, but may require transportation of the patient to the department of radiology which carries a risk of virus spreading in the hospital. On-site chest radiograph is often of such low quality that diagnosis or follow-up will be difficult.

Focused ultrasound examination of the lungs, FLUS, is a diagnostic tool that can show changes in the lung parenchyma due to pneumonia. FLUS is a bed-side examination performed by the physician which results in reduced risk of in-hospital virus contamination. Furthermore, results from FLUS are immediately available to the physician. This allows rapid decision-making which is essential in cases of high patient burdens as seen in the COVID-19 pandemic.

Furthermore, SARS-CoV-2 positive patients with pneumonia may be at higher risk of respiratory failure than those without pneumonia. Identifying patients at high risk can qualify decisions about monitoring level and organization of intensive care resources. Conversely, patient with COVID-19 symptoms but without pneumonic FLUS finding could likely be managed as out-patients. Such a risk-stratification may optimize the allocation of limited healthcare resources and reserve in-hospital capacity to those patients who needs it.

Hypothesis

FLUS can risk-stratify patients with COVID-19 symptoms.

FLUS can predict respiratory failure in patients with COVID-19 pneumonia.

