FLUS can diagnose COVID-19 pneumonia with high sensitivity and specificity using PCR-test and chest radiograph as reference.

Aim

To study the ability of FLUS in COVID-19 to predictive respiratory failure.

To study the diagnostic capability of FLUS to find COVID-19 pneumonia.

To study risk-stratifying capability of FLUS in patients with COVID-19 symptoms.

Method

Design

Multicenter prospective cohort study with convenience sampling.

Setting

Emergency departments or internal medicine departments who admit patients with COVID-19 symptoms.

Participants

Patients who have COVID-19 symptoms and require diagnostic testing.

Patients who have a positive SAR-CoV-2 PCR-test and require admission to hospital.

Inclusion criteria

- Patients who are seen in COVID-clinics or emergency departments due to symptoms that require diagnostic work-up to COVID-19.
- Patients admitted to hospital with positive SARS-COV-2 PCR-test and in whom FLUS is performed less than 48 hours after admission.

Exclusion criteria

- Age less than 18 year.
- Former participation in this study.
- Pre-FLUS ventilator support.

Double inclusion

Inclusion in this study will not restrict patient from inclusion in other studies.

Recruitment

Participants are recruited at the local hospital. In Denmark the study is labelled quality assurance and the need for informed consent is thus waived. Local regulations are followed and it is the responsibility of each inclusion site to achieve appropriate regulatory permissions including need for approval from local ethical committees and healthcare authorities.

Variables

Ultrasound variables: FLUS are performed according to ERS guidelines and to Standard of Operating Procedure specific to this study. Film clips are recorded and saved for later evaluation. 14 zones are scanned. Film clips are marked with scanning position (L1, L2...etc.). If the patient is unable to sit, only anterior and lateral zones are scanned. FLUS findings are assessed on the film clips by an observer blinded to other variables. Findings are coded with 1/0 for presence of pneumonia. Moreover, a scoring system is applied:

FLUS findings	Score
Normal FLUS	0
Interstitial syndrome, defined as more than 3 B-lines in a single zone.	1
Diverse B-lines or irregular pleura	
Interstitial syndrome, defined as more than 3 B-lines in a single zone.	2
Confluent B-lines.	
Consolidations (sub-pleurale, lobar, with or without air-bronchograms)	3

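### No model without FLUS is planned, so the sensitivity, specificity and AUC of the prediction model cannot show how much FLUS adds to bedside predictors

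*Protocol*

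**What the plan says.** The first aim in the protocol concerns FLUS itself: "To study the ability of FLUS in COVID-19 to predictive respiratory failure". The Hypothesis section puts it as "FLUS can predict respiratory failure in patients with COVID-19 pneumonia".

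Under Data analysis, the protocol describes one logistic prediction model. On the outcome it says "Dependent variable is intubation", and on the predictors "Independent variables are age (continuous), FLUS result (Binary or ordinal), SARS-CoV-2 status (Binary) and peripheral oxygen saturation (continuous". The data set is split: "One is used for model development and one is used for validation of the model". Geographic validation and bootstrapping are also planned, and the paragraph ends with "Sensitivity, specificity and ROC AUC is calculated".

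In the SAP, Building Prediction Models has a different covariate list, again with FLUS in it: "The variables are sex, age, relevant comorbidity, oxygen administration and the mean-FLUS score". The SAP's table of regressions has, for ventilator treatment, a univariable model with mean FLUS and a multivariable one: "Variable: respirator_beh Flusmed, alder, køn, sat" (that is, mean FLUS with age, sex and saturation). Similar rows exist for COVID death and intensive care admission.

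No multivariable model in either document omits FLUS. Neither mentions a change in AUC, a likelihood-ratio test, reclassification or any other comparison of models.

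**The concern.** A combined model's AUC belongs to all its predictors together. Saturation (or oxygen need) and age may well predict intubation on their own, and both are recorded at admission. If they carry the discrimination, the combined model will look good whether FLUS contributes or not. Without the same model minus FLUS, the reader has nothing to subtract.

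The protocol's Background motivates FLUS as a way to decide on monitoring level and allocate scarce capacity. For that use, the question is what the scan adds to information the clinician already has. A validated AUC near 0.8 could be read as an achievement of FLUS when it may belong to the other variables. The crude tests (chi-square, t-test or rank-sum, univariable regression) do not settle this, because they tend to be positive whenever FLUS merely tracks hypoxaemia.

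**Working it through.** **Inputs from the documents.** About 20% intubation, 375-400 participants, 10-15 events per variable, 50-75 events, a 5% significance level, and a split into a development and a validation part (fractions not given).

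**The plan's own figure.** N = predictors × events per variable ÷ event rate. With 5 × 15 = 75 events, 75 ÷ 0.20 = 375, which is the stated lower end. (The four predictors that the protocol names would give 40-60 events and 200-300 patients; that mismatch is a separate matter.) At 375-400 patients, 375 × 0.20 = 75 to 400 × 0.20 = 80 events are expected. If the split is equal, which is assumed, each part has about 38-40. The documents give no AUC or target AUC to reproduce.

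**Assumed inputs.** The documents give no effect sizes, no FLUS prevalence and no correlation between FLUS and saturation. Two simulations with different assumptions were therefore used, each comparing the model with FLUS to the same model without it.

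*Simulation A.* Continuous FLUS score; n = 375; 20% events; log odds ratios per SD of 0.8 (age) and -0.9 (saturation); FLUS has no effect of its own but is correlated with low saturation. AUCs are in-sample.

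- Correlation 0.5: mean AUC 0.783 with FLUS and 0.781 without, a difference of 0.002.
- Univariable FLUS is significant in about 40%, 80% and 97% of studies at correlations of 0.3, 0.5 and 0.7.
- The adjusted test of FLUS rejects in about 5% of studies, as it should.
- With weaker covariates (log odds ratios ±0.5), the AUCs at correlation 0.5 are 0.692 and 0.689. Univariable FLUS is significant in 44% at correlation 0.5 and 19% at 0.3.

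*Simulation B.* Binary FLUS (50% positive); n = 400; 20% events; age, saturation and PCR status as the other predictors; fitted in one half, AUC measured in the other; FLUS correlation with low saturation 0 or 0.5.

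| True FLUS odds ratio | Other predictors | AUC without FLUS | AUC with FLUS | Change |
|---|---|---|---|---|
| 1 | weak | 0.69-0.70 | 0.69 | -0.005 to -0.006 |
| 1 | medium | 0.76-0.77 | 0.76 | -0.003 to -0.004 |
| 1 | strong | 0.84-0.85 | 0.84 | -0.003 |
| 2 | medium | 0.77-0.78 | 0.77-0.79 | +0.005 to +0.008 |
| 3 | medium | 0.76-0.79 | 0.78-0.81 | +0.020 to +0.025 |

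A worthless FLUS thus sits in models with validation AUCs from 0.69 to 0.84. That range contains every value seen with a true odds ratio of 2 or 3, so the combined AUC alone cannot separate the cases. At correlation 0.5 and odds ratio 1, the unadjusted chi-square was significant in 53-93% of runs; at correlation 0 it was significant in about 5%. The likelihood-ratio test of FLUS on all 400 patients rejected in 4-7% of runs at odds ratio 1, 60-71% at 2 and 94-98% at 3.

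**How far the AUC difference can be relied on.** In simulation A with a real FLUS effect (log odds ratio 0.49 per SD, correlation 0.5), the adjusted test rejected in about 80% of studies. Half-split validation AUC rose by only about 0.010, with an SD across studies of about 0.015-0.017. The SD exceeds the mean gain, so the difference alone is a weak basis for a conclusion.

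**The case against.** The strongest reply is that the plan already examines FLUS with adjustment. The SAP's regressions include mean FLUS with age, sex and saturation, and the protocol's own model yields an adjusted FLUS coefficient too. The ordinary Wald test of that coefficient agreed with a likelihood-ratio test in 99.7% of simulated null studies. This stands. A reader might infer that all the other evidence on FLUS is univariable, or that the study could not tell a useful test from a redundant one. The documents support neither: adjusted association is planned and is tested at the correct error rate. But a coefficient does not give the gain in discrimination, sensitivity or specificity, and neither document says what role it will play in the conclusion.

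Second, the sentence on sensitivity, specificity and AUC names no model. It follows directly on the model-validation text, so the combined model is the natural reading, but figures for FLUS alone are possible. Those would show crude discrimination and still not what FLUS adds.

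Third, the aim speaks of predicting respiratory failure, not of predicting beyond age and saturation. A finding that tracks hypoxaemia still predicts, and a significant crude test in that setting is a real crude association. This also stands: it would go too far to say that the plan cannot show that FLUS predicts respiratory failure. The objection limits the point to added value, which is what the intended use in allocating resources depends on.

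Finally, the simulated figures rest on assumed effects. The rate of significant crude results does vary widely with them. The near-identical AUCs with and without a null FLUS held in every setting tried.

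**Conclusion.** The point holds in limited form. The planned performance figures, on their natural reading, describe models that always include FLUS, and no reference model is planned, so incremental predictive performance goes unmeasured. Adjusted association is covered, and the crude-association and diagnostic aims are unaffected.

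On size: a FLUS with no effect of its own changes the AUC by 0.006 or less in either direction while the combined AUC ranges from about 0.69 to 0.84. The in-sample pair of about 0.78 with and without FLUS assumes n = 375, 20% events and the log odds ratios given above. The frequency of a significant crude FLUS result (about 40% to 97% in that setting) depends on an assumed correlation of 0.3 to 0.7, so no single rate should be cited.

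This should be corrected before analysis, because a combined AUC is easily credited to the test under study. It does not invalidate the primary chi-square comparison.

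**What to change.** 1. In the development part, fit the same model with and without FLUS on the same patients. Apply both to the validation part without refitting.
2. Report the adjusted FLUS odds ratio with its likelihood-ratio test.
3. Report the change in AUC, both bootstrap optimism-corrected and in the validation part, with a 95% CI.
4. Report both models' sensitivity and specificity at one common cut-off.
5. State that any claim that FLUS adds to bedside predictors rests on the adjusted test together with the change in AUC and its CI. It should rest neither on the combined-model AUC nor on the AUC difference alone.

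The cost is one extra model fit and a few lines in the SAP, with no new data. The change in AUC will be small and imprecise with about 38 events per half (75 ÷ 2, assuming an equal split), so its CI needs to be read with the adjusted test.
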